2.6.2 Statistical hypothesis, model, and method of analysis

For the secondary analysis of UAS7, complete clinical response, controlled disease and AAS7=0, pairwise comparisons of each LOU064 doses to Placebo will be performed. No adjustment for multiple comparisons will be done due to the exploratory nature of this study.

2.6.3 Handling of missing values/censoring/discontinuations

Missing values for binary response like UAS7 = 0 response, UAS7 <=6 response and DLQI 0/1 of secondary analyses will be imputed by non-responder imputation method regardless of the reason for missingness.

2.7 Safety analyses

All safety endpoints (i.e. AEs, laboratory data, vital signs, and ECG as well as potential risks defined in the safety profiling plan) will be summarized by actual treatment group using the safety set.

All data will be included in the analysis regardless of rescue medication use.

2.7.1 Adverse events (AEs)

All information obtained on adverse events will be displayed by treatment group and any LOU064 dose.

Treatment-emergent events are defined as any events started on or after the first dose of study treatment day or any events presented prior to the first dose of study treatment day but increased in severity based on preferred term and before end of the study.

The number (and percentage) of subjects with treatment- emergent AEs will be summarized in the following ways:

- by primary system organ class and preferred term
- by primary system organ class, preferred term and maximum severity
- by Standardized MedDRA Query (SMQ) and preferred term

Summaries will also be presented for AEs by severity and for study treatment related AEs.

Separate summaries will be provided for deaths, SAEs, and other significant AEs such as AEs leading to discontinuation and AEs leading to treatment interruption.

If a subject reported more than one AE with the same preferred term, the AE with the greatest severity will be presented. If a subject reported more than one AE within the same primary system organ class, the subject will be counted only once with the greatest severity at the system organ class level, where applicable.

All AEs and SAEs including the non-treatment emergent AEs will be listed.

2.7.1.1 Adverse events of special interest / grouping of AEs

Crude incidence rate for adverse events of special interest will be provided. The latest project eCRS will be used for reporting.

2.7.2 Deaths

All deaths will be listed and reason for death will be summarized by SOC and PT.

2.7.3 Laboratory data

The summary of laboratory evaluations will be presented for two groups of laboratory tests (hematology and serum chemistry).

Descriptive summary statistics for the change from baseline to each study visit will be presented. These descriptive summaries will be presented by test group, laboratory test and treatment group and any LOU064 dose. Change from baseline will only be summarized for subjects with both baseline and post baseline values.

For each parameter, the maximum change from baseline (maximum decrease and maximum increase) will be analyzed analogously.

Laboratory data will be listed and values outside the normal ranges will be flagged by treatment group, subject, and visit/time for patients who have experienced any abnormalities.

In addition, shift tables will be provided for all parameters to compare a subject's baseline laboratory evaluation relative to the most extreme laboratory test value within a treatment period. For the shift tables, the normal laboratory ranges will be used to evaluate whether a particular laboratory test value is normal, low, or high (including category "high and low"). These summaries will be presented by laboratory test and treatment group.

The following laboratory parameters will be analyzed with respect to numerical Common Terminology Criteria for Adverse Event (CTCAE) grades (version 5.0), given in [Table 2-3](#): hemoglobin, platelets, white blood cell count, neutrophils, lymphocytes, creatinine, total bilirubin (TBL), gamma-glutamyl transferase (GGT), alanine aminotransferase (ALT), aspartate aminotransferase (AST), alkaline phosphatase (ALP).

CTCAE grades based on lab results alone will be applied programmatically, Clinical assessments (in *italic* below) will not be considered. In case of missing baseline laboratory assessment, it will be assumed as normal.

The number and percentage of subjects with CTCAE grade newly occurring or worsening after baseline will be presented. Shift tables will be provided on CTCAE grades. These summaries will be split into hematology and chemistry.

Table 2-2 CTCAE grades for laboratory parameters to be analyzed

[figure not shown]
CTCAE term	Laboratory assessment	Grade 1	Grade 2	Grade 3	Grade 4
Anemia	Hemoglobin (Hgb)	<LLN-10.0 g/dL;	<10.0- 8.0 g/dL;	<8.0 g/dL;	Life-threatening consequences;
Platelet count decreased	Platelet	<LLN-75,000/mm ³ ;	<75,000-50,000/mm ³ ;	<50,000-25,000/mm ³ ;	<25,000/mm ³ ;
White blood cell decreased	White blood cell	<LLN-3000/mm ³ ;	<3000-2000/mm ³ ;	<2000-1000/mm ³ ;	<1000/mm ³ ;
Neutrophil count decreased	Neutrophils	<LLN-1500/mm ³ ;	<1500-1000/mm ³ ;	<1000-500/mm ³ ;	<500/mm ³ ;
Lymphocyte count decreased	lymphocytes	<LLN-800/mm ³ ;	<800-500/mm ³ ;	<500-200/mm ³ ;	<200/mm ³ ;
INR increased	INR	>1.2 - 1.5; >1 - 1.5 x baseline if on anticoagulation ; monitoring only indicated	>1.5 - 2.5; >1.5 - 2.5 x baseline if on anticoagulation ; dose adjustment indicated	>2.5; >2.5 x baseline if on anticoagulation ; bleeding	-
Creatinine increased	Serum creatinine	>1-1.5 x ULN	>1.5 - 3.0 x baseline; >1.5 - 3.0 x ULN	>3.0 x baseline; >3.0 - 6.0 x ULN	>6.0 x ULN
Blood urea Nitrogen (BUN) increased	Urea	>1- 1.5xULN	>1.5 - 3.0 x baseline; >1.5 - 3.0 x ULN	>3.0 x baseline; >3.0 - 6.0 x ULN	>6.0xULN
Blood bilirubin increased	Total bilirubin (TBL)	>ULN - 1.5 x ULN if baseline was normal; > 1.0 - 1.5 x baseline if baseline was abnormal	>1.5 - 3.0 x ULN if baseline was normal; >1.5 - 3.0 x baseline if baseline was abnormal	>3.0 - 10.0 x ULN if baseline was normal; >3.0 - 10.0 x baseline if baseline was abnormal	>10.0 x ULN if baseline was normal; >10.0 x baseline if baseline was abnormal
GGT increased	Gamma-glutamyl transferase (GGT)	>ULN - 2.5 x ULN if baseline was normal; 2.0 - 2.5 x baseline if baseline was abnormal	>2.5 - 5.0 x ULN if baseline was normal; >2.5 - 5.0 x baseline if	>5.0 - 20.0 x ULN if baseline was normal; >5.0 - 20.0 x baseline if	>20.0 x ULN if baseline was normal; >20.0 x baseline if

			baseline was abnormal	baseline was abnormal	baseline was abnormal
Alanine aminotransferase increased	Alanine aminotransferase (ALT)	>ULN - 3.0 x ULN if baseline was normal; 1.5 - 3.0 x baseline if baseline was abnormal	>3.0 - 5.0 x ULN if baseline was normal; >3.0 - 5.0 x baseline if baseline was abnormal	>5.0 - 20.0 x ULN if baseline was normal; >5.0 - 20.0 x baseline if baseline was abnormal	>20.0 x ULN if baseline was normal; >20.0 x baseline if baseline was abnormal
Aspartate aminotransferase increased	Aspartate aminotransferase (AST)	>ULN - 3.0 x ULN if baseline was normal; 1.5 - 3.0 x baseline if baseline was abnormal	>3.0 - 5.0 x ULN if baseline was normal; >3.0 - 5.0 x baseline if baseline was abnormal	>5.0 - 20.0 x ULN if baseline was normal; >5.0 - 20.0 x baseline if baseline was abnormal	>20.0 x ULN if baseline was normal; >20.0 x baseline if baseline was abnormal
Alkaline phosphatase increased	Alkaline phosphatase (ALP)	>ULN - 2.5 x ULN if baseline was normal; 2.0 - 2.5 x baseline if baseline was abnormal	>2.5 - 5.0 x ULN if baseline was normal; >2.5 - 5.0 x baseline if baseline was abnormal	>5.0 - 20.0 x ULN if baseline was normal; >5.0 - 20.0 x baseline if baseline was abnormal	>20.0 x ULN if baseline was normal; >20.0 x baseline if baseline was abnormal

ULN: Upper limit of normal range; LLN: Lower limit of normal range.

For laboratory test values below Lower Level of Quantification (LLQ) or above Upper Level of Quantification (ULQ) will be imputed as LLQ or ULQ value, respectively.

Local lab result due to covid-19 situation will only be listed but not include in the summary table.

Abnormalities in urinalysis result will be summarized by visit separately and listed.

2.7.4 Other safety data

2.7.4.1 ECG and cardiac imaging data

Summary statistics will be provided for ECG parameters by treatment group and any LOU064 dose, and visit/timepoint (pre-dose or 1 hr post-dose). Shifts with respect to normal ranges and number and percentage of notable abnormalities will also be summarized.

Triplicates measurements on ECG are scheduled for some visits. For numeric measurements, the mean of the scheduled measurements will be used. For ECG overall interpretation, most common interpretation (normal/abnormal) of the three assessments taken will be used.

[figure not shown]
PR, QRS, QT, QTcF, and RR intervals will be obtained from 12-lead ECGs for each subject during the study. Frequency tables will be produced for the number and percentage of subjects with notable QT and QTcF intervals and with noteworthy PR, QRS and Heart Rate interval or changes from baseline.

For ECGs, a notable QT and QTcF interval value is defined as:

- QT > 500 msec;
- QTc (Fridericia's) interval > 450 msec (males), QTc (Fridericia's) interval > 460 msec (females);
- QTc (Fridericia's) interval change from baseline > 30 msec, >60 msec;
- PR > 250 msec.

All ECG data will be listed by treatment group, subject and visit/time for patients experienced and ECG abnormalities.

Local ECG data will be included in the summary in case central reading was applied.

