- *Impaired platelet function:* BTK is a signaling kinase in one of several platelet activation pathways. In the prescribing information for both ibrutinib and acalabrutinib, bleeding/bruising events are very common and affecting approximately 50% of patients with hematologic malignancies. Warnings on hemorrhagic events including deaths have also been described (see SmPC for ibrutinib and acalabrutinib). Compared to other drugs in the same class, LOU064 demonstrated a higher selectivity for BTK vs. other TEC kinases. Thus, bleeding may be less a safety concern when compared to ibrutinib and acalabrutinib. Patients receiving LOU064 must be closely monitored for any signs and symptoms of bleeding while in the study. Subjects with a known history of bleeding disorder, subjects taking medication that is known to increase the bleeding risk (other than acetylsalicylic acid), and subjects with an increased thromboembolic risk must be excluded from the study (see details in [Section 5.2](#)).
- *Myelomodulation:* The role of BTK inhibition in myelomodulation is not fully understood. Treatment emergent grade 3 or 4 cytopenias (neutropenia, thrombocytopenia and anaemia) were reported in patients with hematologic malignancies treated with ibrutinib and acalabrutinib (see SmPC for ibrutinib and acalabrutinib). Therefore, patients must be closely monitored for signs and symptoms of cytopenia while in the study, and those with a history of hematological disorders or with markedly altered hematologic parameters at baseline must be excluded from the study (see details in [Section 5.2](#)).
- *Risk of cardiovascular origin:* LOU064 is an *in vitro* inhibitor of the hERG channel protein, without affecting other ion channels.

For ibrutinib, atrial fibrillation was described for 3% to 6% of subjects across multiple trials which might be associated with Na-channel inhibition (see SmPC for ibrutinib). For acalabrutinib, both atrial fibrillation and atrial flutter of any grade were reported in 3% of patients (see SmPC for acalabrutinib). Therefore, an intensive ECG monitoring strategy be implemented in this study (see [Section 8.4.2](#)). In addition, patients with a known history or current diagnosis of ECG abnormalities indicating significant risk of safety will be excluded from the study (see details in [Section 5.2](#)).

- *Drug-drug interactions:*

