6.1.3 Treatment arms/group

Subjects will be assigned at Day 1 to one of the following 7 treatment arms (Table 6-2) in a ratio of 1:1:1:1:1:1:1. Each subject will take 2 capsules in the morning and 2 capsules in the evening at home (except for Week 4 and Week 12 morning dose, which are to be taken on site during the site visit), for a total of 4 capsules daily. Depending on the treatment arm, these capsules will contain LOU064 at different dose strengths or placebo. The patient must take one capsule from each morning bottle (identified with a sun symbol) in the morning and one capsule from each evening bottle (identified with a moon symbol) in the evening.

Table 6-2 Treatment regimen per arm

		Number of capsules per intake per treatment arm						
		Arm A: 10 mg LOU064 qd	Arm B: 35 mg LOU064 qd	Arm C: 100 mg LOU064 qd	Arm D: 10 mg LOU064 bid	Arm E: 25 mg LOU064 bid	Arm F: 100 mg LOU064 bid	Arm G: Placebo
Morning dose	10 mg LOU064	1	1	0	1	0	0	0
	25 mg LOU064	0	1	0	0	1	0	0
	50 mg LOU064	0	0	2	0	0	2	0
	Placebo	1	0	0	1	1	0	2
Evening dose	10 mg LOU064	0	0	0	1	0	0	0
	25 mg LOU064	0	0	0	0	1	0	0
	50 mg LOU064	0	0	0	0	0	2	0
	Placebo	2	2	2	1	1	0	2

Treatment duration

All subjects will receive their respective LOU064 or placebo capsules for 12 weeks (from Day 1 until Week 12).

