8.4.2 Electrocardiogram (ECG)

Standard 12-lead ECGs must be recorded after 10 minutes rest in the supine position according to the ECG investigator manual. The preferred sequence of cardiovascular data collection during study visits is ECG collection first, followed by vital signs, and blood sampling. The Fridericia QT correction formula (QTcF) should be used for clinical decisions.

Triuplicate 12 lead ECGs are to be collected for central analysis as follows:

- Day 1: before administration of the first dose of study medication
- Week 4 and Week 12: before administration of study medication and 1h after administration of the study medication (study medication will be taken at the study site; ECG recording will be accompanied by taking samples for PK analysis (see [Section 8.5.1](#)).

Single 12 lead ECGs will be collected for central analysis at Screening, Week 2, Week 8 and Week 16.

For any ECGs with treatment emergent abnormalities, two additional ECGs must be performed to confirm the abnormal finding and copies forwarded to the central ECG laboratory for assessment. A monitoring or review process should be in place for clinically significant ECG findings throughout the study and especially at baseline before administration of study treatment.

In the event that a clinically significant ECG abnormality is identified at the site (eg severe arrhythmia, conduction abnormality of QTcF > 500 ms or QTcF prolongation > 60 ms), a copy of the assessment is sent to the core laboratory for expedited review if applicable, and the ECG is repeated (and a copy sent to the core laboratory) to confirm the diagnosis. If the subject is hemodynamically compromised, the investigator or a medically qualified person must initiate appropriate safety procedures without delay (for example cardioversion).

Clinically significant abnormalities must be recorded on the eCRF as either medical history/current medical conditions or AEs as appropriate.

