8.4.5 Appropriateness of safety measurements

Given the mild inhibition of hERG channels and the fact that atrial fibrillation/atrial flutter are a known risk for ibrutinib and acalabrutinib, Novartis implements an intensive ECG monitoring strategy in this study to allow proper collection of ECG data together with PK sampling to detect and analyze any potential effect of LOU064 on cardiac function, in particular QTc prolongation. The laboratory evaluation plan will provide sufficient safety information for LOU064 in the target population.

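### At the Day 1, Week 4 and Week 12 triplicates, the majority rule classes a rhythm or conduction abnormality seen on one of three ECG tracings as normal; a by-treatment any-tracing count would recover it

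*SAP*

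**What the plan says.** SAP 2.7.4.1 notes that "Triplicates measurements on ECG are scheduled for some visits". For these it averages numeric measurements, and for the categorical reading it says: "For ECG overall interpretation, most common interpretation (normal/abnormal) of the three assessments taken will be used". ECG summaries are by treatment group, any LOU064 dose and "visit/timepoint (pre-dose or 1 hr post-dose").

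Protocol 8.4.2 sets the schedule. Triplicates are taken on Day 1 before the first dose and at "Week 4 and Week 12: before administration of study medication and 1h after administration of the study medication". The other visits have one tracing: "Single 12 lead ECGs will be collected for central analysis at Screening, Week 2, Week 8 and Week 16".

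On purpose, Protocol 8.4.5 says "atrial fibrillation/atrial flutter are a known risk for ibrutinib and acalabrutinib, Novartis implements an intensive ECG monitoring strategy", and then names QTc prolongation as the particular target. Protocol 4.6 lists cardiovascular risk and says of acalabrutinib that "both atrial fibrillation and atrial flutter of any grade were reported in 3% of patients".

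The notable ECG criteria in SAP 2.7.4.1 are thresholds for QT, QTcF and PR. The section also promises frequency tables for noteworthy PR, QRS and heart rate. It shows no rhythm category.

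**The concern.** Three tracings taken together serve two purposes that need different summaries. For an interval such as QTcF, they are repeated noisy measurements of one quantity, and the mean is the right summary. A rhythm or conduction disturbance may be intermittent: if it is on one tracing it occurred, and two normal tracings do not cancel it. A majority vote treats it as measurement error.

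What is at stake is the by-treatment view of a risk that the protocol names. With about 44 subjects per arm, one subject is 1/44 = 2.3% of an arm, so a single finding classed as normal is visible at the scale of these tables. Both time points that the SAP labels 1 h post-dose fall under the rule. They are the ones paired with PK sampling because cardiovascular effects may follow peak exposure (Protocol 8.5.1, Table 8-10).

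**Working it through.** The plan gives no figure on this point, so there is none to reproduce.

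**1. Where the rule applies (schedule from Protocol 8.4.2).**

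| Time point | Tracings | Majority rule |
|---|---|---|
| Screening | 1 | no |
| Day 1 pre-dose (baseline) | 3 | yes |
| Week 2 | 1 | no |
| Week 4 pre-dose | 3 | yes |
| Week 4, 1 h post-dose | 3 | yes |
| Week 8 | 1 | no |
| Week 12 pre-dose | 3 | yes |
| Week 12, 1 h post-dose | 3 | yes |
| Week 16 (follow-up) | 1 | no |

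After the first dose there are 7 scheduled time points, 4 triplicate and 3 single, giving 4×3 + 3×1 = 15 tracings. Both 1 h post-dose time points are triplicate.

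**2. What the rule does.** Three normal/abnormal readings give 2³ = 8 patterns: 1 with no abnormal reading, 3 with one, 3 with two and 1 with three. The majority rule classes all 3 one-abnormal patterns as normal.

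**3. How much could be hidden.** Let p be the chance that an intermittent abnormality shows on a given tracing. Neither p nor the dependence between tracings is in the documents, so both are assumptions. If tracings are independent:

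- single tracing: p
- majority of three: 3p² − 2p³
- any of three: 1 − (1 − p)³
- hidden by the majority rule: any minus majority

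At p = 0.1 the majority figure is 3(0.01) − 2(0.001) = 0.028, and the any-of-three figure is 1 − 0.729 = 0.271.

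| p | Single | Majority | Any of three | Hidden | Majority's shortfall against single |
|---|---|---|---|---|---|
| 0.1 | 10.0% | 2.8% | 27.1% | 24.3% | 1 − 0.028/0.1 = 72% |
| 0.2 | 20.0% | 10.4% | 48.8% | 38.4% | 1 − 0.104/0.2 = 48% |
| 0.3 | 30.0% | 21.6% | 65.7% | 44.1% | 1 − 0.216/0.3 = 28% |
| 0.5 | 50.0% | 50.0% | 87.5% | 37.5% | 0% |

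In general, p − (3p² − 2p³) = p(1 − p)(1 − 2p), which is positive for p below 0.5. With independent tracings, three ECGs read by majority then detect less than one ECG would. Tracings taken close together are likely to be correlated. If they always agree, all three rules return p and nothing is hidden. At p = 0.1 the shortfall against a single tracing therefore lies between 0 and 72%.

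**4. Which other routes would show the finding.**

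- *Notable and noteworthy intervals:* QT, QTcF, PR, QRS and heart rate, with numeric values averaged over the triplicate. These may catch a sustained conduction delay, but they do not count a rhythm.
- *Adverse events:* clinically significant ECG abnormalities are recorded as medical history or adverse events (Protocol 8.4.2). Treatment-emergent events are tabulated by treatment, preferred term and SMQ (SAP 2.7.1), with crude incidence for events of special interest (SAP 2.7.1.1). Findings not judged clinically significant do not enter.
- *Listing:* SAP 2.7.4.1 lists ECG data for patients with abnormalities. A listing gives no count by dose, and the SAP does not say whether abnormality there is judged per tracing or on the majority result.
- *Confirmatory ECGs:* Protocol 8.4.2 requires two more after any treatment-emergent abnormality. The SAP does not say how they enter the summary.

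What remains uncounted is a rhythm or conduction finding on one of three tracings that is not reported as an adverse event.

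**The case against.** The strongest reply is that a normal/abnormal field never yields a count of atrial fibrillation under any rule, and that the named risk is measured in the adverse event, SMQ and special-interest tables, all by treatment. The safety profiling plan and the project's case retrieval strategy, to which the SAP refers, are not part of these documents and may cover arrhythmia. This largely stands, and it confines the loss to findings not reported as adverse events.

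A reader might infer that the triplicates were added because of atrial fibrillation. Protocol 8.4.5 does not say so. It gives fibrillation/flutter as one reason for the monitoring as a whole and singles out QTc, for which averaging is right.

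It can also be said that p and independence are assumed. That stands too: the calculation shows the direction and the bounds, not the size in this trial.

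Replacing the majority rule by worst-of-three is tempting but debatable. It would class more Day 1 triplicates as abnormal, which removes those subjects from normal-to-abnormal shifts. It can also widen the mismatch with single-ECG visits. At p = 0.3 the ratio is 30/21.6 = 1.4 under majority and 65.7/30 = 2.2 under worst-of-three; at p = 0.2 it is 20/10.4 = 1.9 and 48.8/20 = 2.4. Only at lower p does it narrow: at p = 0.1 it is 10/2.8 = 3.6 and 27.1/10 = 2.7.

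None of this supplies a by-treatment count of rhythm findings at tracing level.

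**Conclusion.** The point holds in a limited form. At the Day 1, Week 4 and Week 12 triplicates, a rhythm or conduction abnormality on one of three tracings is classed normal in the overall interpretation, and the visible ECG summaries have no rhythm row to recover it. The number of subjects affected cannot be derived from the documents: it is none if tracings agree fully and larger the more independent they are.

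Two stronger readings are not supported.

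- *That every ECG after dosing is affected.* Three of the seven scheduled time points are single tracings. Doses are taken "in the evening at home (except for Week 4 and Week 12 morning dose, which are to be taken on site", so the Week 2 and Week 8 single ECGs may also follow that day's dose. Nor can one say that an abnormal single ECG always counts, because the SAP is silent on whether the two confirmatory ECGs enter the classification.
- *That atrial fibrillation would go uncounted.* A clinically significant episode is recorded as an adverse event and tabulated by treatment.

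This is a modest gap in a descriptive safety summary. It is worth closing because the risk is named and the remedy is cheap.

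**What to change.** In SAP 2.7.4.1, keep the mean for numeric intervals and keep the majority rule for the overall interpretation. Add, by treatment group and for any LOU064 dose, the number and percentage of subjects with a new atrial fibrillation/flutter or other rhythm or conduction finding on any post-baseline tracing. Define new as absent from all baseline tracings, and say whether the Screening tracing is included. Count each single tracing of a triplicate and the confirmatory ECGs.

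Cost: SAP wording and one table row. No new collection should be needed, since the ECGs already go for central analysis; this assumes that the central reader's findings are transferred per tracing, which should be confirmed. Some minor isolated findings will be counted. With 15 scheduled tracings after first dose against 3 on Day 1, some intermittent findings will also look new by chance. The same rule and schedule hold in every arm, so placebo supplies the reference.
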